Sodium Oxybate in Treatment-Resistant REM Sleep Behavior Disorder
(RBD): A Randomized Placebo-Controlled Trial

Study Protocol

NCT04006925

July 8, 2020

Sodium Oxybate in Refractory REM Sleep Behavior Disorder: A Randomized Controlled Study.

Summary

Rapid eye movement sleep behavior disorder (RBD) is a condition resulting in violent dream-enactment during sleep which affects millions of individuals in the United States, however therapies for RBD are limited and cause significant side effects. As a result, despite using a combination of drugs, a large number of patients with RBD continue to act out violent dreams causing severe self-injuries or injuries to their bed partners. Prior studies and our own experience at Stanford have shown that sodium oxybate (SXB) can be effective in these cases of refractory RBD. This study would therefore evaluate the efficacy and tolerance of SXB in this patient population.

We propose to conduct an 8-week trial comparing SXB versus placebo randomly assigned to patients with refractory RBD, i.e. individuals who have insufficiently responded or tolerated melatonin and clonazepam. To strengthen the study design, we will use a double-blind design, and not only measure treatment efficacy based on patients, partners and clinicians report—as done in most studies; we will record RBD objective outcomes with actigraphy, a recently validated objective tool for tracking RBD activity "in vivo". In addition, our study will include the gold standard PSG-based REM activity based on video and EMG activity before and after intervention.

In summary, this study would not only address an important question from a clinical and public health perspective, it would also be the first double-blind randomized controlled study measuring a treatment response based both on clinical and physiological outcomes. We believe that this particular design should pave the way for future trials in RBD.

Scientific Basis/Rationale

Rapid eye movement (REM) sleep behavior disorder (RBD) is a neurological condition resulting in loss of muscle atonia during REM sleep (also called REM sleep without atonia, RWA) leading to violent and injurious dream-enactment behaviors¹. The prevalence of RBD is estimated to be 0.5-1% in the general population^{2,3}, which represents over 2 million individuals in the United States. RBD is strongly associated with synucleinopathies, namely Parkinson's disease (PD), dementia with Lewy bodies (DLB) and multiple system atrophy (MSA). In the remaining individuals, RBD is called "isolated", but is in most cases a prodromal symptom of neurodegenerative disease. While first episodes of dream-enactment can occur decades before neurodegenerative disease, the median time between a formal diagnosis of RBD and phenocconversion is less than 10 years⁴. Other than safety measures, the current evidence suggests melatonin (MLT) or clonazepam (CLZ) as treatment "options" due to incomplete efficacy and possible side effects⁵. The efficacy of CLZ is estimated to be about 80% in the largest case series, but this drug is often associated with limiting side effects. The data on MLT


Taken together, this suggests that SXB may be a viable treatment option in patients with isolated RBD or RBD associated with PD, who have failed MLT and CLZ due to lack of efficacy or intolerance.

Hypothesis

We hypothesize that nightly dose of SXB will result in reduction of RBD severity and frequency per patients report and objective polysomnographic and actigraphic (wrist-worn device) measures, over an 8-week double blind intervention comparing SXB and placebo (PBO). Additionally, we hypothesize that SXB improves sleep quality, and

reduces daytime sleepiness in subjects with RBD associated with a neurodegenerative condition.

Primary Objective

1. Reduction in RBD episodes frequency and severity (RBD log)

Secondary Objectives

1. Improvement in clinical global impression scores per patient and clinician (CGI- efficacy scale, CGI-E, and CGI-impression scale, CGI-I, respectively)
2. Reduction of RWAi by PSG
3. Reduction in movements severity and frequency during REM sleep by quantitative video-PSG analysis¹⁶
4. Changes in overall subjective sleepiness by Epworth sleepiness scale (ESS) and one hour after rise time by Karolinska scale
5. Tolerance and side effects to SXB and PBO

Exploratory Objectives

1. Reduction in "activity score" and "activity index" as measured by actigraphy¹⁷
2. Reduction in periodic limb movement (PLM) arousal index
3. Improved sleep quality by Pittsburgh Sleep Quality Index (PSQI)
4. Effects on mood measured by PHQ-9
5. Effects on anxiety measured by GAD-7
6. Effect on orthostatic heart rate and blood pressure (response to orthostatic maneuver)

[figure not shown]
Trial Design

The total duration of this randomized, double-blind, placebo-controlled trial will be 2 years. For each participant the total duration of the study will be 14 weeks, including 8 weeks of intervention with SXB or PBO, preceded by a 4-week period of collection of baseline data, and followed by a 2-week period of data collection post-intervention. Subjects taking MLT or any other medication capable of affecting RBD other than clonazepam (CLZ) will maintain their regimen at fixed dose throughout the 14-week duration of the study. Those taking CLZ will proceed to reduction and discontinuation of CLZ, followed by a 2-week washout period prior to receiving study drug. If unable to discontinue CLZ prior to study drug, they will reduce CLZ to lowest acceptable dose by the end of the 4-week baseline period followed by cross-taper with SXB during the first 2 weeks of flexible dosing.

In each arm, dosage of SXB and PBO will be titrated up weekly (this weekly titration will occur via phone calls by the PI on days 2-6 after each new dose change) by up to 1.5g nightly dose increments from an initial 4.5g total nightly dose (which could be given

in two unequal doses if needed, or one single dose no greater than 4.5g) to an optimal individual dose based on clinical response on RBD symptoms and tolerability, to a maximum nightly dose of 9g ("flexible dose" period lasting up to 8 weeks). The optimal dose for each participant will then be continued for at least 4 weeks ("stable dose").

Flowchart

MOCA: Montreal Cognitive Assessment

PSG: Polysomnography

CGI: Clinical Global Impression questionnaires

- **Day 1 (Visit #1 = Initial visit with research coordinator):**
 - Verification of inclusion and exclusion criteria
 - Enrollment (if not performed prior)
 - Physical Exam (MoCA,
 - PSQI, PHQ-9, GAD-7, SCOPA-AUT, Epworth sleepiness scale
 - provide RBD logs and sleep diary for the 14 following weeks, 2 blank Karolinska scales, and two actigraphy devices (Philips Actiwatch2) to be worn on dominant wrist and ankle for one month

- instructions on when to complete Karolinska scale #1 (Day 21-27, one hour after waking up the day prior to sleep study) from home
 - Instructions on clonazepam taper, when applies
 - pregnancy testing for female subjects of childbearing age, when applicable
 - collection of adverse events (AEs)
 - MD (PI, coPI) will be available as needed via telephone or remote video conference system
- **Day 1-28 (phone calls, weekly, when applicable):** guidance on downtitration of CLZ
- **Day 28 ± 7 days:** 1st video-PSG wearing home actigraphy device (Philips Actiwatch2) and additional wrist and ankle high-frequency actigraphy device (Xiaomi Amazfit Arc)
- **Day 29 (One day after Day 28 ± 7 days, Visit #2 = Randomization visit with research coordinator):**
 - Collection of 1-month RBD log and sleep diary
 - Collection of Karolinska scale #1
 - Collection of all actigraphy devices
 - Epworth sleepiness scale
 - Randomization
 - Subjects receive SXB or PBO and instructions on titration schedule
 - pregnancy testing for female subjects of childbearing age, when applicable
 - collection of adverse events (AEs)
 - MD (PI, coPI) will be available as needed via telephone or remote video conference system

Day 30-84 ± 7 days (phone calls): Every week after each new dose the subject will be called (including when the dose will remain stable), these phone calls will be made between day 2-6 to discuss response, record adverse events, and determine the next weeks titration dose.

- **Day 57-85 ± 7 days (Visit #3 = Interim visit with research coordinator):**
 - Collection of 1-month RBD log and sleep diary
 - Epworth sleepiness scale
 - PSQI, PHQ-9, GAD-7
 - Completion of CGI-E by participants
 - Completion of CGI-I by clinician
 - Physical Exam (including MoCA, orthostatic vital signs)
 - instructions on when to complete Karolinska scale #2 (Day 78-84, one hour after waking up the day prior to sleep study) from home
 - Participants provided with two actigraphy devices (Philips Actiwatch2) to be worn on dominant wrist and ankle for one month
 - pregnancy testing for female subjects of childbearing age, when applicable

- Collection of AEs, side effects
- MD (PI, coPI) will be available as needed via telephone or remote video conference system

- **Day 84-112 ± 7 days: 2nd video-PSG wearing home actigraphy device (Philips Actiwatch2) and additional wrist and ankle high-frequency actigraphy device (Xiaomi Amazfit Arc)**

- **Day 85-113 (One day after Day 84-112 ± 7 days, Visit #4 = Final Visit with research coordinator):**
 - Collection of high-frequency actigraphy device (Xiaomi Amazfit Arc)
 - Collection of 1-month RBD log and sleep diary
 - Collection of AEs, side effects
 - Collection of Karolinska scale #2
 - Epworth sleepiness scale
 - PSQI, PHQ-9, GAD-7, SCOPA-AUT
 - Completion of CGI-E by participants
 - Completion of CGI-I by clinician
 - Physical Exam (including MoCA,
 - Verification of any protocol deviation (e.g., change in drug regimen that could affect RBD outcome)
 - Discontinuation of treatment
 - MD (PI, coPI) will be available as needed via telephone or remote video conference system

- **Day 99-127 ± 7 days (Visit #5 = Follow-up Visit with research coordinator):**
 - Collection of AEs
 - Collection of actigraphy devices
 - Collection of 2-week RBD log and sleep diary
 - Compensation
 - End of study
 - MD (PI, coPI) will be available as needed via telephone or remote video conference system

Treatment Regimen

Being diagnosed with "refractory RBD", all participants will have received and failed prior treatments with CLZ and MLT prior to being eligible for the study. Treatment failure is defined as insufficient efficacy, or intolerance to treatment limiting the possibility of uptitration or leading to discontinuation, resulting in persistent of RBD episodes averaging 2 per week or 8 per month or greater.

At study entry, we expect most participants to currently be treated with CLZ and/or MLT. Subjects taking MLT or any other medication capable of affecting RBD other than CLZ will maintain their regimen at fixed dose throughout the 14-week duration of the study. In subjects treated with CLZ, CLZ will be titrated down and discontinued 2 weeks prior to start of study drug, or when unable to be discontinued, cross-tapered during the first 2 weeks of receiving study drug until reaching the lowest possible CLZ dose, which will then be continued until the end of the stable dosing period

Participants will be randomized in a double-blind manner to either SXB or PBO. The duration of the intervention in both conditions will be no longer than 12 weeks, including up to 8 weeks of flexible dosing and 4 weeks of stable dosing. Treatment will be initiated with 4.5g dose of SXB or PBO, given nightly in two doses 2.5-4h apart according to the standard protocol used in narcolepsy. PBO will be similar in appearance, smell and flavor to the subjects, so that the investigators and participants will be unable to distinguish it from SXB. The dose will be increased or decreased by 0.5 - 1.5g weekly increments until reaching the optimal dose based on clinical response and tolerance, not exceeding 9g nightly. Evidence has shown that patients with RBD treated with sodium oxybate respond to nightly doses ranging from 3-6 g. Among these subjects, some have benefited from a 5 gram nightly dose. This flexibility in dosage is determined on an individual basis, in which the final dose must be both effective and tolerated. Dosage flexibility is essential as this older population with prodromal or overt signs of neurodegeneration may not require or tolerate the higher dosages used in patients with narcolepsy. Although the “default” regimen will be two equally divided doses 2.5-4hours apart, if required, the drug will be given in two unequal doses, or in one single dose, with no single dose allowed to be greater than 4.5g. Once optimal dose reached, fixed dose will be continued for at least 4 weeks and discontinued over one night. During the two weeks following discontinuation, data will continue to be collected. Patients will be allowed to resume usual treatment, including CLZ.

In this study, the choice of flexible dosing for patients receiving SXB is based on a few factors. From the 4 case reports summarized above, effective doses of SXB in patients with refractory RBD ranged from 3g to 6g nightly, one patient requiring uptitration of his initial 5g dose to 6g. No adverse events or side effects were reported by the authors. In patients with narcolepsy, the efficacy of SXB is dose-dependent, showing superior efficacy with 9g nightly dose compared to 6g. Taken together, this data suggests that higher SXB doses will be more likely to control RBD symptoms, however with a higher risk of side effects. In the two studies evaluating SXB efficacy and tolerance in patients with PD using flexible dosing, final mean doses were 7.8g and 4.8g^{14,15}.

Our study will include a mixed group of participants, some with a neurological diagnosis of PD and some otherwise healthy individuals. We identify risk of dizziness and falls as the most concerning risk in patients with a diagnosis of synucleinopathy, as this could be aggravated by SXB. We will therefore carefully exclude from this study any participant who already suffers from balance impairment resulting in falls or requiring an ambulating device, as well as any patient with symptomatic orthostatic hypotension. Taken all these considerations into account, and given the expected interindividual variability regarding

optimal dose of SXB, we chose flexible dosing for highest clinical benefit while minimizing the risk of side effects.

The total amount of SXB for the 12 participants randomized to active drug is: 5,292g.
The total amount of PBO for the 12 participants randomized to placebo drug is: 5,292g.

Option for “Rescue” Open Label Extension Period

All participants, should they decide to drop out of the study, may become eligible for a “Rescue” open label extension period, during which they will receive open label active drug sodium oxybate in an unblinded fashion. This will provide patients the opportunity of experiencing benefit from the study drug. Such participants would then receive ascending doses of sodium oxybate, according to the protocol, and will also be asked to present for visits and second polysomnography starting at visit 2, otherwise required by the protocol until the end of the study.

Inclusion Criteria

- Adult patients aged 40 to 85 years
- Women may be included only if they have a negative β -HCG test at screen; are sterile (documented hysterectomy, bilateral oophorectomy, or bilateral salpingectomy, or congenitally sterile) or postmenopausal (no menses for 12 months without alternative medical cause).
- Women with childbearing potential whose male partners are potentially fertile must use one of the following highly effective birth control methods for the duration of the study (ie, starting at screening) and for 30 days after last dose of study drug
 - estrogen-progestin oral contraceptive pills, patches, or vaginal ring
 - progestogen pills, implant or injection
 - intrauterine device (IUD)
 - intrauterine hormone-releasing system (IUS)
 - bilateral tubal occlusion
 - vasectomised partner (the sole sexual partner who has received medical assessment of the surgical success)or
 - abstain from heterosexual intercourse
- In individuals without a diagnosis of Parkinson's disease (PD), PSG-confirmed “definite RBD” per the International Classification of Sleep Disorders, 3rd edition (ICSD-3)
- In individuals with a diagnosis of PD, either PSG-confirmed diagnosis of RBD ("definite RBD") or history of dream-enactment ("probable RBD")
- RBD episodes ≥ 2 /week or ≥ 8 /month (defined as vocalization and/or limb or body movements attributed to dream-enactment)
- Reliable reporting by bed witness in the absence of patient awareness

Exclusion Criteria

- History of falls during ambulation in the last 6 months despite adequate neurologic treatment
- Requirement of an ambulatory device at home
- Inadequately treated symptomatic orthostatic hypotension (syncopal episode in the last 6 months)
- BMI > 35
- Untreated or uncontrolled OSA (4% desaturation AHI>15)
- Liver impairment
- Renal impairment
- Congestive heart failure
- Uncontrolled hypertension
- Treatment with valproic acid
- Current history of NREM parasomnias or parasomnia overlap syndrome (at least 2 episodes in the last 6 months)
- Diagnosis of narcolepsy
- Cognitive impairment resulting in inability to comply with treatment instructions
- Diagnosis of any dementia including dementia with Lewy bodies
- Diagnosis of multiple system atrophy
- RBD attributed to a CNS lesion
- PD Hoehn and Yahr stage 4 and 5
- Any change of PD regimen during the study period
- Current alcoholism or prior history of drug abuse
- Pregnancy
- Epilepsy currently treated with sedating antiepileptic drugs;
- Concomitant use of other CNS depressants, including but not limited to opioid analgesics, benzodiazepines other than clonazepam, muscle relaxants, and/or illicit CNS depressants
- Current depression (at least PHQ-9 score = 10), history of psychosis
- Any change of antidepressant regimen during the study period
- Chronic severe RLS (iRLS>20) (at least 3 days per week)
- Succinic semi-aldehyde dehydrogenase deficiency (SSADH)

Primary Endpoint

- Number of RBD episodes in one month (RBD log), last month of treatment compared to 1-month baseline

Secondary Endpoints

- Severity of RBD episodes in one month (RBD log), last month of treatment compared to 1-month baseline. Severity is scored from 1 to 3 (1: least severe, 3 most severe):
 1. non injurious behaviors: facial expressions, non-aggressive vocalizations (mumbling, gentle talking, casual conversation, singing, laughing...), twitches, gentle shaking, non-aggressive movements of fingers, arms or legs...;

2. potentially injurious: punching, kicking, arm flailing or thrashing around, at least one limb or head out of bed, sitting up in bed, crawling, attempting to stand up or leave bed, near falls, cursing, screaming, shouting, yelling, or any behavior requiring bed partner to wake up participant;
 3. injurious: any contact with bed partner (hitting or grabbing), wall or furniture, any fall or leaving bed (doving out, walking, jumping).
- CGI efficacy scale (CGE-E): 4-point therapeutic effect scale and 4-point side effect scale, jointly filled by patient and partner on last day of treatment
 - CGI improvement scale (CGI-I): 7-point improvement scale filled by clinician on last day of treatment
 - RWAi according SINBAR criteria comparing PSG pre-intervention to PSG post-intervention
 - video-PSG analysis of REM related vocalizations and movements (“simple” versus “complex”) as per Sixel-Döring and colleagues¹⁶
 - Sleep outcomes: EDS, Karolinska 1 h after awakening

Exploratory Endpoints

- “Activity index” as recorded by actigraphy¹⁷ (percentage of 30-second epochs with an activity score above zero) last month of treatment compared to 1-month baseline
- Sleep outcomes: PSQI
- Cognitive outcome: MoCA
- Mood and Anxiety: PHQ-9 and GAD-7
- Orthostatic vital signs

Sample Size Justification/Statistical Analysis

Sample size calculation was made for the outcome of number of RBD episodes per month. Based on the data published by Brunetti et al.¹⁸, the number of RBD episodes decreased from 11.2 \pm 5.2 at baseline to 10.3 \pm 3.7 per month in the placebo arm. To detect an effect size of 50% reduction in the number of RBD episodes per month ([placebo-active]/placebo) with a power of 80% and alpha of 5%, the number of participants would need to be 10 per arm. Based on prior studies using SXB in subjects with PD, a conservative drop out rate of 15-20% could be anticipated^{14,15}, which would require to enroll at least 24 participants, i.e. 12 participants per arm.

Reporting to Jazz Pharmaceuticals

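### PSQI, PHQ-9 and GAD-7 are measured before treatment only on Day 1, ahead of the clonazepam taper, so within-arm change on these exploratory scales includes clonazepam reduction; repeat them at Visit 2

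*Protocol*

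**What the plan says.** **Protocol, Flowchart, Day 1 (Visit 1).** The questionnaires are "PSQI, PHQ-9, GAD-7, SCOPA-AUT, Epworth sleepiness scale". The same visit includes "Instructions on clonazepam taper, when applies".

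**Protocol, Flowchart, Days 1 to 28.** Weekly phone calls give "guidance on downtitration of CLZ".

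**Protocol, Trial Design.** The rule for clonazepam (CLZ) is: "Those taking CLZ will proceed to reduction and discontinuation of CLZ, followed by a 2-week washout period prior to receiving study drug". Participants who cannot stop go to the lowest acceptable dose by the end of baseline, "followed by cross-taper with SXB during the first 2 weeks of flexible dosing".

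**Protocol, Flowchart, Day 29.** The entry headed "Visit #2 = Randomization visit with research coordinator" covers the log and diary, "Collection of Karolinska scale #1", the actigraphy devices, the Epworth scale, randomisation, dispensing, pregnancy testing and adverse events. PSQI, PHQ-9 and GAD-7 are not listed. They reappear at Visits 3 and 4.

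**Protocol, Exploratory Endpoints.** PSQI is a sleep outcome, followed by "Mood and Anxiety: PHQ-9 and GAD-7".

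**SAP.** Secondary and exploratory outcomes are analysed per protocol. Change within each arm and the difference between arms are both tested. No covariate or stratification for clonazepam use is described, and no baseline is defined for these scales.

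**The concern.** A baseline should describe the participant as they are when randomised treatment starts. For a clonazepam user, the only earlier value of these three scales is taken on the entry dose, and every later value is taken on study drug with clonazepam stopped or reduced. Reducing a benzodiazepine could plausibly move sleep quality, mood and anxiety, although the documents give neither a direction nor a size. A paired test within the SXB arm cannot separate that movement from an effect of SXB, and a paired test within the placebo arm cannot separate it from a placebo response.

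Sleep quality is part of the Protocol's stated hypothesis, and PSQI is its instrument. Daytime sleepiness, in the same hypothesis, does get a randomisation-day value through the Epworth scale. The documents give no reason for treating the two differently.

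**Working it through.** **1. Timing, from the written visit lists** (one figure is missing from the text available, so the check rests on the lists).

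| | Visit 1 | Visit 2 | Visit 3 | Visit 4 |
|---|---|---|---|---|
| PSQI, PHQ-9, GAD-7 | yes | no | yes | yes |
| Epworth | yes | yes | yes | yes |
| Clonazepam, if used at entry | entry dose | stopped or reduced | stopped or reduced | stopped or reduced |
| Study drug | none | dispensed | on | on |

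Visit 2 falls one day after Day 28 ± 7, so between Day 22 and Day 36. The gap from Day 1 is 29 − 1 = 28 days, range 22 − 1 = 21 to 36 − 1 = 35. For the Epworth scale at Visit 2 the gap is 0.

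**2. Arm sizes.** The plan gives no figure for these scales. Its 10 per arm for the primary endpoint reproduces: 50% of 10.3 is 5.15 episodes, and with SD 3.7, two-sided 5% alpha and 80% power the t-test solution is 9.17, rounded up to 10. Enrolment is 12 per arm. These two numbers serve below only as arm sizes.

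**3. Within-arm change.** Let p be the share of an arm on clonazepam at entry and w the shift from clonazepam reduction, in SDs of change among non-users. With no drug effect:

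- mean change = p × w
- SD of change = √(1 + p(1 − p)w²)

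The documents give neither p nor w. The assumed ranges are p = 0.25 to 0.75 and w = 0.3 to 0.8.

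| p | w | Mean change (SD) | Rejection, n = 10 | Rejection, n = 12 |
|---|---|---|---|---|
| 0.25 | 0.3 | 0.25 × 0.3 = 0.075 | 5.5% | 5.6% |
| 0.50 | 0.5 | 0.50 × 0.5 = 0.25 | 10.6% | 12.0% |
| 0.75 | 0.8 | 0.75 × 0.8 = 0.60 | 36% | 43% |

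The last two columns show how often a nominal 5% paired t-test declares a change when the drug does nothing.

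**4. Between-arm contrast.** The taper before randomisation contributes w × (p in SXB arm − p in placebo arm). Randomisation makes the expected difference in p equal to 0, so the expected contribution is 0. Chance imbalance remains. With 12 per arm, the hypergeometric probability of a gap of 4 or more users between arms is 0.15 if 6 or 18 of the 24 are users, and 0.22 if 12 are. The SD of the resulting shift in the contrast is about w√(2p(1 − p)/12), from 0.3 × √(2 × 0.25 × 0.75/12) = 0.05 to 0.8 × √(2 × 0.5 × 0.5/12) = 0.16 SD of change.

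**The case against.** The strongest reply is that the trial's question is SXB against placebo. The Day 1 to 28 taper precedes randomisation and is the same in both arms, and the placebo arm exists to show change not caused by the drug. This stands. A reader might infer that the timing could hide or create an SXB effect relative to placebo. The documents do not support that: the expected contribution to the contrast is zero, leaving noise and chance imbalance. The per-protocol set used for these outcomes weakens the protection of randomisation somewhat, but that is a separate matter.

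Two further inferences also go too far:

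- **That every clonazepam user completes a taper and washout between the first two values.** Those who cannot stop have no washout and continue reducing after study drug starts.
- **That Visit 3 always follows at least four weeks of study drug.** The nominal interval is 57 − 29 = 28 days. With the ±7-day windows, Day 50 is 21 days after Day 29 and 14 days after a Visit 2 on Day 36.

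The size is also uncertain. The Treatment Regimen section expects most participants to enter on clonazepam, melatonin or both, without giving the clonazepam share. Some will already have stopped clonazepam because they did not tolerate it.

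The reply does not rescue the within-arm tests, which the SAP runs and which randomisation does not protect.

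**Conclusion.** The point holds for within-arm change on PSQI, PHQ-9 and GAD-7 in participants taking clonazepam at entry. That change cannot be read as an effect of SXB or placebo alone. Under the assumed ranges the distortion runs from negligible (0.075 SD, 5.5% rejection) to substantial (0.60 SD, 36% with 10 per arm); the documents do not allow a narrower statement.

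For the SXB-placebo contrast the finding is weaker: no expected bias, a baseline 21 to 35 days old, and exposure to chance imbalance in clonazepam users. The loss of precision from the older baseline cannot be quantified from the documents.

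These are exploratory scales, and the primary and secondary endpoints do not use them. The Epworth scale is repeated at Visit 2 and the first Karolinska scale is completed on Days 21 to 27, so the problem does not extend to them in the same way. MoCA and SCOPA-AUT do share the Day 1-only baseline. This is a cheap improvement, not a threat to the trial's main conclusion.

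**What to change.** Add PSQI, PHQ-9 and GAD-7 at Visit 2, before study drug is dispensed, and state in the SAP that the Visit 2 value is the baseline for these endpoints. Keep the Day 1 values for eligibility (PHQ-9) and description.

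The SAP is dated January 2023 and written in the past tense, so the visits may be over. If Visit 2 values were not collected, base inference on the between-arm contrast adjusted for the Day 1 score and clonazepam use at entry. Report the number of clonazepam users per arm, and do not interpret within-arm change as a drug effect.

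**Cost:** three self-completed questionnaires at an existing visit, a few minutes per participant.

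**Limits:** a Visit 2 baseline may still carry residual withdrawal effects, in which case later recovery could look like benefit within an arm. It also does not separate the cross-taper in participants who cannot stop clonazepam before study drug. That reduction comes after randomisation and could differ by arm, so these participants should be identified in the report.

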Sodium Oxybate in Treatment-Resistant REM Sleep Behavior Disorder (RBD): A Randomized Placebo-Controlled Trial

Statistical Analysis Plan

NCT04006925

January 11, 2023

Statistical analysis (using SAS 9.4, Cary, NC) was by intention-to-treat for the primary efficacy analysis, comparison of baseline characteristics, safety and tolerance and per-protocol (PP) for secondary/exploratory analyses. PP analysis included all participants who completed titration and the 4-week treatment period. Sample size calculation was based on a prior randomized controlled study by Brunetti et al.²⁵ To detect an effect size of 50% reduction in the number of RBD episodes per month ([placebo - active] / placebo) with a power of 80% and alpha of 5%, the number of participants needed to be 10 per arm. Anticipating a dropout rate of 20%, 24 participants required to be enrolled.

We tested the primary hypothesis that SXB is superior to placebo in reducing the number of RBD episodes from baseline, as observed in the last month of treatment using linear mixed effects models with random intercepts. Models were parameterized in two ways to estimate separate group trajectories and between-group differences in change over time. Cohen's d was calculated as a measure of treatment effect size. Similar hypotheses were tested on secondary and exploratory outcomes. Within- and between-group differences were assessed with paired- and unpaired t-tests, or with the Wilcoxon Signed Rank and Mann-Whitney U tests for nonnormal data. Bootstrapped percentile-based 95% confidence intervals were calculated based on 10,000 randomly resampled datasets. Participants scoring below 4 on the CGI-I and CGI-E were classified as "responders"; chi-square tests were performed to compare the proportion of responders between groups. All statistical tests were conducted using a 2-sided alpha level of 0.05. For secondary/exploratory analyses, bootstrapped percentile-based 95% confidence intervals were calculated based on 10,000 randomly resampled datasets. Descriptive statistics on safety data are provided for all randomized participants (intention-to-treat), by treatment group and study phase.

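### Weekly adverse-event calls are fixed to Day 30-84 although dosing may run to Day 113, so longer titrators have fewer scheduled contacts at their stable dose

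*Protocol*

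**What the plan says.** Protocol, Flowchart: the calls carry a calendar window, "Day 30-84 ± 7 days (phone calls): Every week after each new dose the subject will be called". The sentence goes on "including when the dose will remain stable), these phone calls will be made between day 2-6 to discuss response, record adverse events", and adds that the calls also settle the following week's dose. Study drug is handed out at Visit 2 on Day 29 ("Subjects receive SXB or PBO and instructions on titration schedule"). Visit 3 falls on Day 57-85, and Visit 4 on Day 85-113 ("One day after Day 84-112 ± 7 days, Visit #4 = Final Visit with research coordinator"). Adverse events are collected at Visits 3, 4 and 5, and a physician can be reached remotely as needed.

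The protocol gives two lengths of dosing. Treatment Regimen says "no longer than 12 weeks, including up to 8 weeks of flexible dosing and 4 weeks of stable dosing", and the titration paragraph of Trial Design likewise allows up to 8 flexible weeks followed by at least 4 stable ones. The opening of Trial Design describes a 14-week study "including 8 weeks of intervention with SXB or PBO", and the Hypothesis section also speaks of 8 weeks.

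The SAP summarises safety descriptively for all randomised participants, "by treatment group and study phase". Tolerance and side effects are a secondary objective of the protocol.

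**The concern.** Visit 3, the second sleep study, Visit 4 and Visit 5 all have day ranges that move with the length of titration. The call window does not. A participant who reaches a stable dose early is called every week until treatment ends. One who titrates for longer passes some or all of the stable phase after the last scheduled call, even though the same sentence says calls continue at a stable dose.

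Titration length is decided after randomisation, on response and tolerability. How often a participant is asked about adverse events would therefore depend on a post-randomisation course that treatment itself may influence. The thinner contact falls at the final titrated dose, and the protocol itself expects more side effects at higher doses. With 12 participants per arm, a few long titrators could shift the stable-phase counts.

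**Working it through.** **Inputs.** Dosing starts on Day 29 (Flowchart, Visit 2). The flexible period lasts f weeks, at most 8, and the stable period is taken as 4 weeks (Treatment Regimen). Calls are one per dosing week, with the last on or before Day 84 (Flowchart).

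**Reproducing the plan's dates.**
- Start of stable phase = 29 + 7f.
- Visit 4 = 29 + 7f + 28.
- f = 4: stable phase starts on Day 57, Visit 4 on Day 85.
- f = 8: stable phase starts on Day 85, Visit 4 on Day 113.

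These are the two ends of the stated ranges for Visit 3 (57-85) and Visit 4 (85-113). The visit schedule therefore fits 4 to 8 weeks of titration followed by 4 stable weeks.

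**Calls in the stable phase.** Day 29 to Day 84 is 56 days, or 8 dosing weeks. Stable-phase calls = 8 − f, limited to between 0 and 4. If the 7-day tolerance moves the last call to Day 77 or Day 91, the 8 becomes 7 or 9.

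| Flexible weeks | Stable phase (days) | Calls, last on Day 84 | Calls, last on Day 77 / 91 | Stable days after Day 84 |
|---|---|---|---|---|
| 4 | 57-84 | 4 | 3 / 4 | 0 |
| 5 | 64-91 | 3 | 2 / 4 | 7 |
| 6 | 71-98 | 2 | 1 / 3 | 14 |
| 7 | 78-105 | 1 | 0 / 2 | 21 |
| 8 | 85-112 | 0 | 0 / 1 | 28 |

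If the tolerance only carries forward the 7-day allowance on the Day 28 sleep study, dosing moves with it and the nominal column applies. At nominal days the flexible phase has one call per week for everyone.

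**Scheduled contacts for an 8-week titrator.** Adverse events are collected at Visit 3 (Day 85) and Visit 4 (Day 113), with no scheduled call between: 113 − 85 = 28 days. A 4-week titrator has the same two visits with 4 calls between them.

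**Under the 8-week text.** Day 29 + 56 = Day 85, so calls to Day 84 cover all dosing. The drug supply also fits that length on one path. The supply is 5,292 g / 12 = 441 g per participant, and 7 × 4.5 + 7 × 6 + 7 × 7.5 + 35 × 9 = 441 g over 56 nights. Extending that path to 84 nights gives 126 + 63 × 9 = 693 g each, or 8,316 g for 12. This is a consistency check only: 441 g over 84 nights would be a mean of 5.25 g, so the supply does not exclude a longer course.

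**The case against.** The strongest reply is that this is a symptom of the unreconciled 8- versus 12-week duration and not a separate decision about safety monitoring. Day 84 suits the 8-week text. The second Karolinska instruction is likewise still at Day 78-84, although the second sleep study spans Day 84-112, so the schedule looks only partly updated. The wording about stable doses shows an intent to keep calling. This stands as an account of the probable cause. It does not remove the point: changing the stated duration to 12 weeks alone would leave the call window as it is, and staff following the calendar would stop at Day 84.

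Three stronger readings are tempting, and the documents do not support them.

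- A reader might infer that long titrators in general have no stable-phase calls. That holds at nominal days only for the full 8 weeks. The documents do not say how many participants titrate that long, and three steps of 1.5 g take the dose from 4.5 g to 9 g, so 8 weeks need not be typical.
- A reader might infer that adverse-event capture stops. It does not: Visits 3 and 4 bracket the stable phase, Visit 5 follows, and a physician is available. What is lost is frequency, with recall of up to 4 weeks instead of 1.
- A reader might infer that the safety tables are biased between arms. That needs titration length to differ by arm, and no figures are given. The tables are descriptive and the SAP does not define study phase, so flexible versus stable is a natural reading but not a stated one. Any percentage for under-reporting would rest on assumed recall probabilities, so none is given here.

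**Conclusion.** The point holds as an internal contradiction with a limited consequence for harms data. Followed literally, scheduled stable-phase calls fall from 4 to 0 as titration lengthens from 4 to 8 weeks, leaving up to 28 days between scheduled contacts. Adverse-event ascertainment therefore varies with titration length. An effect on the tables by arm and phase is possible but not shown.

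This rests on nominal days, a 4-week stable phase, the longer of the two dosing durations, and phase meaning flexible versus stable. Under the 8-week text the gap disappears. It should be put right because tolerance is a secondary objective and the correction is small.

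**What to change.** Reconcile the Day 30-84 call window with the dosing durations in the Hypothesis, Trial Design, Flowchart and Treatment Regimen sections, and with the protocol's own statement that calls continue at a stable dose, so that adverse-event recording covers the same dosing period for every participant. The calls also set the next dose, so which duration and contact schedule apply is for the sponsor and investigator to decide; no clinical rule is proposed here.

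In the SAP, define study phase, and report the number of adverse-event contacts by arm and phase beside the safety tables. The SAP is written in the past tense; if conduct is complete, this reporting step can still be taken.

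The cost is a schedule amendment and, if calls follow the longer dosing period, at most 4 further calls for a participant with an 8-week titration. The ceiling is 4 × 24 = 96 calls, reached only if every participant titrates for 8 weeks.
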